5.6.6 Electrocardiograms

Descriptive statistics for ECG parameters and changes from baseline at each scheduled visit will be presented.

Shift tables will be presented for the changes from baseline in ECG findings (categorized as normal; abnormal, not clinically significant; and abnormal clinically significant) for each scheduled visit.

In addition, the number (percentage) of subjects with at least 1 postbaseline abnormal ECG result in QTc Fridericia or QTc Bazett during treatment will be summarized. Clinically abnormal ECG results in QTc will be categorized as follows:

- Absolute QTc interval prolongation:
 - QTc interval >450 msec
 - QTc interval >480 msec
 - QTc interval >500 msec
- Change from baseline in QTc interval:
 - QTC interval increases from baseline >30 msec
 - QTC interval increases from baseline >60 msec

A subject listing will also be provided.

5.6.7 Other Safety Analyses

5.6.7.1 Karnofsky Performance Status

Karnofsky performance status (KPS) will be summarized by a shift table from baseline to worst postbaseline scale.

5.6.7.2 Left Ventricular Ejection Fraction

LVEF (%) assessed on echocardiogram or MUGA scans will be summarized. The lowest postbaseline value and change from baseline will be summarized descriptively.

In addition, LVEF quantitative values will be classified into the following 5 categories:

- Hyperdynamic = LVEF greater than 70%
- Normal = LVEF 50% to 70% (midpoint 60%)
- Mild dysfunction = LVEF 40% to 49% (midpoint 45%)
- Moderate dysfunction = LVEF 30% to 39% (midpoint 35%)
- Severe dysfunction = LVEF less than 30%

A shift table from baseline to the worst postbaseline values may be generated.

5.7 Other Analyses

5.7.1 Health-Related Quality of Life

The analysis of HRQoL will be performed on the QoL Analysis Set.

For HRQoL analysis, summary statistics of the scores for the derived functional/symptom scales according to the scoring manual and global health status scores will be summarized by treatment arm at each time point. A separate prespecified HRQoL analysis following FDA and EMEA PRO Guidelines will be performed and detailed in a separate SAP and HRQoL report. Scoring of EQ-5D-3L and derivation of utility for health economic analysis will also be accomplished in a separate analysis and described in a separate HRQoL report.

5.8 Exploratory Analyses

5.8.1 Efficacy Analysis Based on IIR Assessment

The efficacy endpoints ORR_{24W} , ORR, and PFS based on blinded IIR assessment will be defined and analyzed in the same manner as those based on the investigator assessments that described in [Section 5.4](#).

5.8.2 Exploratory Analysis for Subjects with Prior PD-1/PD-L1 Treatments

Exploratory analysis on efficacy endpoints of PFS and OS may be performed descriptively for the subjects who had prior PD-1/PD-L1 treatments.

The subgroup analyses on the efficacy endpoint ORR and primary safety endpoint for the subjects with prior PD-1/PD-L1 treatment are specified in [Section 5.4.4](#).

5.8.3 Biomarker-related Analysis

For the biomarker-related exploratory analysis, such as the analyses to explore the associations between blood biomarker and efficacy-related endpoints and the development of exposure/biomarker/clinical endpoint models (whenever possible, using a mechanism-based approach) for both efficacy and safety data, the analysis methods will be specified in a separate analysis plan.

Other exploratory analyses may be conducted as appropriate.

6 INTERIM ANALYSES

Two interim analyses will take place when 150 and 200 total subjects in the Per-Protocol Analysis Set 1 have completed 24 weeks follow-up or discontinue earlier. Each interim analysis will test both non-inferiority and futility of lenvatinib 14 mg arm ORR_{24W} compared to lenvatinib 18 mg arm ORR_{24W} based on investigator assessment. An O'Brien-Fleming stopping boundary (Lan and DeMets, 1983; DeMets and Ware, 1980) will be used for efficacy. An interpolated non-binding stopping boundary will be used for futility, which will spend $\beta=0.005$ and $\beta=0.10$ at the first and second interim analyses, respectively.

The stopping boundaries on the P value scale and the cumulative error probabilities spent at each interim analysis and final analysis are shown in Table below. For example, at the second interim analysis, non-inferiority in ORR_{24W} will be claimed if the 1-sided P value is ≤ 0.014 ; futility will be claimed if the 1-sided P value is ≥ 0.207 .

Analysis #	Cumulative α Spent	Efficacy Boundary (P value)	Cumulative β Spent	Futility Boundary (P value)
Interim Analysis #1	0.005	0.005	0.005	0.776
Interim Analysis #2	0.015	0.014	0.10	0.207
Final Analysis	0.05	0.045	0.2	0.045

Safety and efficacy monitoring will be performed by an independent DMC. The function and membership of the DMC are described in the DMC charter. The recommendations concerning continuation or termination of the trial, or regarding modification of the trial or informed consent documents will be reached by the DMC based on the review of study safety and efficacy data. Determination of whether lenvatinib 14 mg can be used as an alternative dosing strategy will be based on clinical judgment by the Sponsor in consultation with the independent DMC (as specified in the DMC charter) by assessing risks and benefits according to the totality of data at either of the interim or final analyses.

The interim analyses together with the safety monitoring DMC analyses will be performed by an independent statistical reporting team, such as a statistical contract research organization.

DMC meetings for the two protocol specified interim analyses have been carried out on 13 Mar 2019 and 12 Jun 2019. The DMC reviewed the interim analyses results and the study continues as planned.

7 CHANGES IN THE PLANNED ANALYSES

Not applicable.

8 DEFINITIONS AND CONVENTIONS FOR DATA HANDLING

8.1 Visit Windows

Visit windows will be defined to be upper and lower bounds of 3 days of the scheduled visit, following the protocol, which states that efforts should be made to conduct study visits (and safety assessments) on the day scheduled (± 3 days).

Tumor assessments are to be performed every 8 weeks (during the 8th week, starting from the date of randomization), or sooner if clinically indicated, until progressive disease during Randomization Phase. If a subject discontinues from study treatment without disease progression, tumor assessments should continue to be performed every 8 weeks until documentation of disease progression or beginning a new anticancer treatment during Follow-up Period.

In the calculation of descriptive statistics for laboratory values and vital signs, if a visit has multiple observations, the observation closest in date and time to the target visit day will be used in the analysis. If two or more observations have the same distance to the target visit day, the one that has the highest CTCAE grade or is furthest away from the normal range will be used.

The purpose of this windowing is to provide a single record per subject per visit for the calculation of descriptive statistics per scheduled visit, and change from baseline per visit. Other safety analyses (eg, worst grade laboratory results and shift tables) will include all postbaseline assessments, including those scheduled and unscheduled visits.

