9.4.2.7 Management of Blood Glucose and Lipids

Hyperglycemia, hyperlipidemia, and hypertriglyceridemia are recognized class effects of rapamycin derivatives, including everolimus. Glycemic and lipids control should be optimized before starting a subject on this study.

Blood glucose will be monitored as specified in the Schedule of Procedures/Assessments. For subjects with blood glucose > ULN, a fasting (>6 h, water only) blood glucose sample will be obtained. Grading according to CTCAE v4.03 will be based on the fasting blood glucose result. The choice of hypoglycemic agent should be individualized to the subject's clinical circumstances and follow standard medical practice.

Dose alterations of everolimus may be required in accordance with prescribing information.

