Other	Albumin, cholesterol, glucose ^c , lactate dehydrogenase, total protein, triglycerides, amylase, lipase, creatine kinase Serum or urine pregnancy test ^d (β-hCG or hCG)
Urine Dipstick Testing ^e	glucose, hemoglobin (or blood), ketones, pH, protein ^f , specific gravity

Category	Parameters
RBC = red blood cell, WBC = white blood cell, INR = International Normalized Ratio.	

 a. INR should only be performed as part of the screening assessment and when clinically indicated. b. Free T4 and TSH levels will be performed at the Screening Visit, at the Baseline Visit (or within 72 hours prior to the first dose of study drug). TSH levels will be repeated at Day 1 of every other cycle (starting with Cycle 2) and at the Off-Treatment visit. c. For subjects with blood glucose >ULN, a fasting (>6 h, water only) blood glucose sample will be obtained. d. For women of childbearing potential (ie, premenopausal women and postmenopausal women who have been amenorrheic for less than 12 months) e. If urine dipstick testing suggests a urinary tract infection, a urinalysis with microscopy and/or urine culture with sensitivities should be considered, if clinically indicated, at the institution's laboratory. f. If urine protein by dipstick is $\geq 2+$ (first occurrence or a subsequent increase in severity of urine dipstick proteinuria occurring on the same lenvatinib dose level), then a 24-hour urine collection should be done to quantify the 24-hour urine protein excretion. 	

All hematology, clinical chemistry (including pregnancy test, as applicable), and urine samples are to be obtained prior to study drug administration and results reviewed prior to administration/dispensing of study drug at the beginning of Cycle 1, and within 48 hours of Day 1 in each treatment cycle and within 72 hours of Day 1 after the data cutoff for the primary analysis. Refer to [Table 2](#) for management of clinically significant laboratory abnormalities.

A laboratory abnormality may meet the criteria to qualify as an AE as described in this protocol (see [Section 9.5.1.4.1](#) and the CRF Completion Guidelines. In these instances, the AE corresponding to the laboratory abnormality will be recorded on the Adverse Event CRF.

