9.7.1.7.1 PHARMACOKINETIC/PHARMACODYNAMIC ANALYSES

Lenvatinib and everolimus exposure parameters (AUC or concentration at the time of the event or cumulative AUC, as appropriate) derived from the population PK analysis will be related to biomarker, safety, and efficacy data using a model-based approach. For some PK/PD analyses, data from this study will be pooled with data from the Phase 2 Study E7080-G000-205 (Study 205).

For the exposure-response relationship for biomarkers (e.g., VEGF, Ang-2), data will be analyzed using a model-based approach with indirect PK/PD models.

For efficacy, a tumor growth inhibition model based on longitudinal tumor size measurements of target lesions will be included. Study drug exposure for lenvatinib and everolimus and/or measured biomarkers (e.g., VEGF, Ang-2) will be investigated as predictors and/or correlations with tumor burden changes in the tumor growth inhibition model, whenever possible using a mechanism-based approach.

Other analyses will include logistic regression analysis for ORR_{24w}, KM plots of PFS data, and Cox-regression analysis. For the Cox-regression analysis of PFS, adjustment will be made for subject's baseline characteristics or tumor-related features. In addition to lenvatinib and everolimus exposure, changes in biomarker concentrations and/or tumor burden will be related to PFS, whenever possible using a mechanism-based approach.

For the exposure-response relationship of safety, the model-based analysis will include the following AEs: hypertension (systolic and diastolic BP), triglyceridemia (and cholesterolemia), glycemia, proteinuria, weight loss, fatigue, nausea, vomiting and diarrhea. For hypertension, triglyceridemia (and cholesterolemia) and glycemia, data will be analyzed using an indirect-response model. For proteinuria, urine dipstick and/or 24-hour urine data will be analyzed using a longitudinal categorical logistic regression analysis with Markov element. For weight loss, fatigue, nausea, vomiting, and diarrhea, data will be analyzed using a longitudinal categorical logistic regression analysis. For time to treatment discontinuation due to an AE and time to first dose reduction, KM plots stratified by lenvatinib exposure will be prepared.

Population PK and PK/PD analyses will be detailed in a separate analysis plan.

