5.6.4 Laboratory Values

Laboratory results will be summarized using Système International (SI) units. Laboratory values that are non-missing and reported as ‘below the detectable limit’ of an assay will be replaced by half the detectable limit in the summary tables. Central laboratory test results will be used as the primary data source for laboratory analyses. Only when the central laboratory tests results are missing, the local laboratory test results will be used as substitute.

On-treatment laboratory tests will be defined as the laboratory tests conducted from the start of treatment to no more than 28 days after the last dose of study treatment.

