5.6.4.1 Hematology and Clinical Chemistry

Laboratory parameters will be graded based on CTCAE Version 4.03. In the summary of laboratory parameters by CTCAE grade, for parameters with CTCAE grading in both high and low direction (eg, calcium, glucose, magnesium, potassium, sodium), CTCAE grades in both high and low directions will be summarized separately.

The evaluation of clinical laboratory tests will focus on the following selected laboratory analytes:

Hematology Panel:

- hematocrit, hemoglobin, red blood cell (RBC) counts, white blood cell (WBC) count, absolute neutrophil count, and absolute lymphocyte count, platelet count

Chemistry Panel:

- Electrolytes: bicarbonate, calcium, chloride, magnesium, phosphate, potassium, sodium
- Liver function tests: alanine aminotransferase (ALT), alkaline phosphatase, aspartate aminotransferase (AST), direct bilirubin, total bilirubin
- Renal function tests: blood urea/blood urea nitrogen (BUN), creatinine
- Thyroid function tests: thyroid stimulating hormone (TSH), free T4 level
- Other: albumin, cholesterol, triglycerides, glucose, calcium, lactate dehydrogenase (LDH), amylase, lipase, creatine kinase

Descriptive statistics for values and changes from baseline at each scheduled visit for hematology and chemistry laboratory parameters will be provided. Box plots of laboratory values over time will also be provided for selected hematology and chemistry parameters.

In addition, the worst CTCAE grade in hematology and chemistry during the treatment will be summarized by treatment arm and CTCAE grade. Shift tables from baseline to the worst CTCAE grade during treatment will be generated.

Subjects with treatment-emergent markedly abnormal values (TEMAV) will be summarized. Treatment-emergent markedly abnormal value is defined as a value that is outside of the normal range and the CTCAE grade increased from baseline by 2 or more grades, except for phosphate which must have shifted by 3 or more grades.

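### The SAP's worst-grade and shift tables for glucose include non-fasting values, although the protocol bases the CTCAE glucose grade on the fasting sample

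*SAP*

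**What the plan says.** **Protocol.** Section 9.4.2.7 (Management of Blood Glucose and Lipids) gives the trigger, "For subjects with blood glucose > ULN, a fasting (>6 h, water only) blood glucose sample will be obtained", and then the grading rule: "Grading according to CTCAE v4.03 will be based on the fasting blood glucose result". The synopsis repeats both. The trigger also appears in 9.5.1.4.3, Table 5 footnote c ("For subjects with blood glucose >ULN, a fasting (>6 h, water only) blood glucose sample will be obtained"), and in Table 6 footnote k. Nothing in the protocol requires routine on-study chemistry to be drawn fasting.

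**SAP.** Section 5.6.4.1 grades laboratory parameters by CTCAE v4.03 and names glucose among those graded both ways: "for parameters with CTCAE grading in both high and low direction (eg, calcium, glucose, magnesium, potassium, sodium". It plans that "the worst CTCAE grade in hematology and chemistry during the treatment will be summarized by treatment arm and CTCAE grade", followed by shift tables from baseline and a TEMAV summary. For glucose, a TEMAV is a value outside the normal range whose grade has risen by at least 2 from baseline. Section 8.1 sets which records enter: "Other safety analyses (eg, worst grade laboratory results and shift tables) will include all postbaseline assessments, including those scheduled and unscheduled visits". Section 8.2 takes the most recent available value up to first dose as baseline. SAP 5.6.4, 5.6.4.1, 8.1 and 8.2 contain no fasting rule, fasting flag or glucose exception.

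**The concern.** The protocol uses two steps for glucose: a screening value that may be non-fasting, then a fasting sample that decides the grade. The SAP treats both records as equally gradable and keeps the higher. The confirmatory sample then has no effect on the table, because a normal re-draw cannot lower a maximum.

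Hyperglycemia is named in Protocol 9.4.2.7 as a class effect of rapamycin derivatives, including everolimus. Whether the 14 mg start is usable is to be judged on the totality of safety and efficacy data (Protocol 9.7.1.6.1). A laboratory table that counts values the protocol would not grade is a poor input to that judgment, and it could disagree with investigators' grades assigned under the fasting rule.

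**Working it through.** No figure in the plan depends on this point, so the check is a comparison of rules.

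**Step 1: one subject under each rule.** A scheduled non-fasting glucose is above ULN and carries grade g ≥ 1 if graded as it stands. The fasting re-draw is normal.

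| Rule | Records that set the high-direction grade | Result |
|---|---|---|
| Protocol 9.4.2.7 | Fasting re-draw only | Grade 0 |
| SAP 5.6.4.1 with 8.1 | Both records; maximum kept | max(g, 0) = g |

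**Step 2: direction for the worst-grade table.** Let P be the records gradable under the protocol and A all post-baseline records. P is contained in A, so max over A ≥ max over P for every subject. Including the non-fasting values can raise a subject's worst high-direction grade or leave it unchanged, but cannot lower it. It leaves it unchanged when the subject's own fasting grade is already as high.

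**Step 3: direction for shift tables and TEMAV.** These depend on baseline as well. The grades below are illustrative.

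- *Post-baseline value non-fasting.* Fasting grades are 0 at baseline and 0 afterwards, but a non-fasting record grades 2. The table shows a shift of 0 to 2, and 2 − 0 = 2 meets the TEMAV threshold. This is overstatement.
- *Baseline value non-fasting.* The fasting grade at baseline is 0, but the record used grades 1. A true fasting grade 2 follows. The real rise is 2 − 0 = 2, a TEMAV; the tabulated rise is 2 − 1 = 1, not a TEMAV. This is understatement.

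SAP 8.2 selects baseline by timing alone. A fasting re-draw before first dose would be used only because it came last. If none was taken in time, the non-fasting value stands.

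**Step 4: what is not touched.** The primary safety endpoint counts subjects with intolerable Grade 2 or any Grade 3 or higher treatment-emergent adverse event. Those are events reported and graded by the investigator; under Protocol 9.5.1.4.1 the investigator decides whether a laboratory finding is an adverse event. SAP-derived laboratory grades do not enter it. Low-direction glucose is also outside the point, since the re-draw follows only a high value.

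**Step 5: size.** This would need the rate at which non-fasting values exceed ULN while the paired fasting value is normal, and the within-subject correlation of such values. The documents give neither, so no figure is offered.

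**The case against.** The strongest reply is that the SAP is silent on fasting and does not contradict it. It grades by CTCAE v4.03, the protocol says how that applies to glucose, and the sentence in SAP 8.1 appears under visit windows to ensure unscheduled visits are kept. The protocol's own laboratory analysis section (9.7.1.8.3) also plans shifts to worst post-baseline grade with no fasting restriction, and SAP Section 9 leaves derivations to separate specifications.

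Part of this stands: the gap lies partly in the protocol, and the specifications might contain a filter. It does not remove the conflict. Section 9.7.1.8.3 does not withdraw the grading rule in 9.4.2.7. A fasting filter in the specifications would go against the SAP's explicit inclusion of all post-baseline assessments. SAP Section 7 declares no change to the planned analyses.

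It is also fair that the outputs are descriptive, that both arms start everolimus at the same dose, and that everolimus events of special interest have their own summaries (SAP 5.6.3.11). This limits the weight of the point.

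Several stronger readings are tempting but not supported:

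- *The tie-break towards the highest grade in SAP 8.1 adds to the problem.* It governs only the single record per visit for by-visit statistics, not worst grade or shifts.
- *A local fasting re-draw is discarded.* SAP 5.6.4 says "Only when the central laboratory tests results are missing, the local laboratory test results will be used as substitute". It does not say that a central value from one draw cancels a later local draw, and a normal re-draw cannot lower the maximum anyway.
- *The glycemia model will absorb meal effects.* Protocol 9.7.1.7.1 says "For hypertension, triglyceridemia (and cholesterolemia) and glycemia, data will be analyzed using an indirect-response model", but details are left to a separate plan that may handle fasting status.
- *Lipids have the same conflict.* A fasting entry threshold exists, but nothing requires on-study lipid grades to be fasting.
- *A false-positive rate can be computed from the number of draws.* That needs an assumed per-draw rate and independence between draws, neither of which the documents support.

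**Conclusion.** The point holds as a conflict between Protocol 9.4.2.7 and SAP 5.6.4.1 with 8.1. As written, the SAP tabulates a high-glucose grade for a subject whose fasting re-draw was normal, where the protocol assigns none. The error in the worst-grade table can only be upward. For shift and TEMAV tables the net direction is unknown because SAP 8.2 has the same gap.

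The effect is confined to descriptive laboratory tables, and its size is unknown. A reader might infer that the primary safety comparison is biased, or that an arm difference in hyperglycemia is diluted by a known amount. The documents support neither: the first uses investigator-graded events, and the second would need rates that are not given. The conclusion assumes that some on-study samples are non-fasting, which the re-draw procedure implies, and that the unseen dataset specifications follow the SAP as written.

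**What to change.** Amend three SAP sections together:

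- **5.6.4.1:** high-direction glucose grades for the worst-grade, shift and TEMAV outputs use the fasting result, central or local, wherever a fasting re-draw was obtained after a value above ULN. State how a re-draw is paired with the value that triggered it, since the protocol sets no interval. Show values above ULN with no fasting re-draw in a separate non-fasting or unconfirmed category.
- **8.1:** add the glucose exception to the sentence on inclusion of all post-baseline assessments.
- **8.2:** apply the same rule to the baseline glucose grade.

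Carry a fasting flag in the laboratory analysis dataset. Low-direction glucose and all other parameters stay as planned.

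The cost is SAP wording and one programming flag; sample size, alpha and treatment are unaffected. The downside is incomplete information. Protocol 11.5 lists sampling date and time among data recorded directly on the CRF but does not mention fasting status. Re-draws without a recorded status need a query or fall into the separate category. A new collection field would not help for samples already taken; SAP Section 6 records that the second interim review was held on 12 Jun 2019, before this SAP version.
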